10.0 ENDPOINT DEFINITIONS AND CRITERIA FOR EVALUATION

10.1 Endpoint Definitions:

10.1.1 Primary endpoint:

Best overall response rate (ORR) which will include complete responses (CR) and partial responses (PR) as measured by standard criteria (Cheson *et al*, 2014).

10.1.2 Secondary Endpoints:

- 1. Time to treatment failure (TTF)
- 2. Progression-free survival (PFS)
- 3. Overall survival (OS)
- 4. Adverse events (AEs) as measured by NCI-CTCAE 4.0.
- 5. Disease control rate (CR+PR+SD>3 months)

Clinical endpoints of ORR, CR, PR, TTF, PFS and AEs will be stratified by gender.

10.2 Selection of Indicator (Target) Lesions

Up to six of the largest dominant nodes or tumor masses selected according to all of the following:

- Clearly measurable in at least two perpendicular dimensions
 Abnormal lymph nodes are those that are either
 >1.5 cm in the greatest transverse diameter (GTD) regardless of the short axis diameter, or 1.0 cm in short axis diameter regardless of long axis
- If possible, they should be from disparate regions of the body
- Should include mediastinal and retroperitoneal areas of disease whenever these sites are involved
- Extranodal lesions within the liver or spleen must be at least 1.0 cm in two perpendicular dimensions.

10.3 PET Scans

Visual assessment currently is considered adequate for determining whether a PET scan is positive. A Deauville score should be reported. In brief, a positive scan is defined as focal or diffuse FDG uptake above background in a location incompatible with normal anatomy or physiology.

10.4 Response Criteria

Response will be defined by standard NCI criteria (Cheson *et al*, 2014) for lymphoid malignancies [18].

10.5 Progression-free Survival (PFS)

PFS will be measured as time from first study drug administration to the first occurrence of disease progression or death from any cause. Data for subjects without disease progression or death will be censored at the date of last disease assessment or date last known to be alive, respectively. The estimates will be formed using the all treated population. Progression-free survival will be calculated using assessments by investigators. Kaplan-Meier methodology will be used to estimate event-free curves and corresponding quartiles (including the median).

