7.3 Prophylaxis

No prophylactic therapy is required for enzalutamide. Supportive care should be provided as clinically indicated.

7.4 Criteria for removal from protocol treatment:

- Documented progression of disease (see section 10.4).
- Development of seizures, or any therapy-related non-hematologic grade ≥ 4 toxicity or other serious adverse event as defined in section 12.0 will qualify for consideration of removal from protocol treatment.
- Development of any other unacceptable toxicity.
- Delay of treatment for more than 21 days due to toxicity.
- The patient may withdraw from the treatment at any time for any reason.
- Taking prohibited medications concurrent with enzalutamide therapy may result in removal from protocol treatment.

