- ⁵Research Labs include blood samples for serum hormone levels (DHT, DHEA, Androstenedione, Estrone). To be drawn at screening, after 4 weeks of treatment (+/- 6 days), after 12 weeks of treatment (+/- 6 days), and then every 12 weeks (+/- 6 days) during treatment. ⁶ May be obtained up to 8 weeks in advance of initiation of therapy (provided no additional anti-cancer therapies are administered during the interval). A Deauville score should be assigned.
- ⁷ At the beginning of therapy (within 3 days), then every four weeks for the first 12 weeks (+/- 6 days), then at a minimum of every 12 weeks (+/- 6 days) while on therapy, depending on clinical course. For the first day of therapy, pre-entry H&P, PS, disease assessment, and adverse event assessment may be used (these do not need to be repeated within 3 days) and labs done within 14 days are acceptable.
- ⁸ During treatment, restaging CT imaging will be performed every 12 weeks of therapy (+/- 7 days), or as indicated to evaluate clinical suspicion of disease progression. First restaging CT (three months after initiating therapy) should include PET imaging to ascertain metabolic response to therapy. Subsequently, restaging PET/CT should also be performed to confirm metabolic CR in patients with stable PR on 2 consecutive CT staging exams or in patients with a CR based on CT staging and baseline FDG-avid disease to determine metabolic CR and CR (resp.). A Deauville score should be assigned when restaging PET is performed.
- ⁹ Post therapy evaluation will be completed 30 days (+/-7 days) after the last dose of enzalutamide or prior to initiation of new therapy, whichever comes sooner.
- ¹⁰Long-term follow-up should be performed according to the patient's physician's standard of care. This may be performed at patients' local physician's offices. Long-term follow-up will assess survival and disease progression; subjects may be contacted by the study team until five years out from study completion, subject withdrawal of consent, lost to follow-up, or study termination by the investigator, whichever occurs first.
- ¹¹ When appropriate, archival tissue or fresh samples from clinical biopsies may be used.

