11.0 STATISTICAL CONSIDERATIONS

The primary objective of this pilot trial is to derive an estimate of the overall response rate (ORR, see section 10.4) in this population. Secondary clinical endpoints will include time to progression, progression-free survival, and safety. The study is not formally powered to reject a specified null hypothesis and as such the sample size is not based on the number of patients needed to reject the null hypothesis under a specified alternative. That said, with 20 patients the estimated ORR will be within 0.11 of the true ORR if the hypothesized ORR is 20%. An ORR of 20% will be taken as a benchmark for success for the primary endpoint of this pilot study. If the observed ORR is at least 20% (4 or more responses among the 20 patients), we would consider this treatment sufficiently meritorious to warrant further study in a future Phase II trial that will formally evaluate potential efficacy. If the true ORR is 10%, then the probability of 4 or more responses among 20 patients is only 0.13; if the true ORR is 30%, then the probability of 4 or more responses among 20 patients is 0.89. As stated above, the sample size for this trial is not based on specific null and alternative hypotheses. That said, if the assumed-true ORR with this regimen is 35%, then 20 patients will provide 86% power to observe a statistically significant (at the one-sided significance level of .15) improvement in ORR compared to the fixed ORR of 15%.

We will also be encouraged if patients have prolonged disease stability/lack of progression that may be observed with a cytostatic biological agent, though this secondary endpoint will deemed exploratory. For this secondary endpoint, a median PFS of ≥ 6 months would also be scored as a pilot success.

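### The PFS censoring rule gives two dates for the same patient; choosing the date last known alive can only raise the median PFS that section 11.0 scores as a success

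*Combined protocol and SAP*

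**What the plan says.** Section 10.5 defines the endpoint: "PFS will be measured as time from first study drug administration to the first occurrence of disease progression or death from any cause". The next sentence gives the censoring rule: "subjects without disease progression or death will be censored at the date of last disease assessment or date last known to be alive, respectively". The analysis is Kaplan-Meier in all treated patients, with the median reported.

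Section 11.0 attaches a threshold to the result: "a median PFS of ≥ 6 months would also be scored as a pilot success". It also limits the weight of that result, "though this secondary endpoint will deemed exploratory". No confidence limit is required.

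The study calendar (section 9.0) governs how far apart the two dates can be:

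- Note 8: "During treatment, restaging CT imaging will be performed every 12 weeks of therapy".
- Note 9: "Post therapy evaluation will be completed 30 days (+/-7 days) after the last dose of enzalutamide", or before new therapy if that comes sooner.
- Note 10: "Long-term follow-up will assess survival and disease progression; subjects may be contacted by the study team until five years out from study completion". This follow-up is by the local physician's standard of care, with no imaging schedule.

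Section 7.4 foresees patients stopping without progression: for toxicity, for a toxicity delay of more than 21 days, or by choice ("The patient may withdraw from the treatment at any time for any reason").

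**The concern.** The sentence pairs one date with absence of progression and the other with absence of death. PFS is a composite, so every censored patient meets both conditions. The pairing therefore does not separate two groups of patients; it gives two dates to one group. No other section sets an order between them, and overall survival, listed in section 10.1.2, has no censoring rule of its own.

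The choice matters because the date last known alive says nothing about progression. A patient who stops treatment after a clean scan and is later only known to be alive would be counted as progression-free for months in which nobody may have looked. That biases the curve upward. It bears on a named success threshold, in a trial of 20 patients where a few patients decide on which side of 6 months the median falls. If the rule stays open, the date could be picked after the data are seen.

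**Working it through.** **Plan's own figure.** The plan gives no operating characteristic for the median-PFS criterion, so there is none to reproduce. Its ORR figures for the rule of 4 or more responses in 20 do reproduce (0.133 and 0.893, against 0.13 and 0.89 stated) and do not depend on censoring.

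**Inputs from the documents.** 20 patients and a threshold of 6 months (section 11.0); CT every 12 weeks on therapy, one visit 30 days (+/-7) after the last dose, then standard-of-care follow-up (section 9.0, notes 8 to 10); accrual of about 1 patient per month (section 11.2).

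**Step 1: direction.** The Kaplan-Meier estimate is S(t) = product over event times of (1 − d/n), where d is the number of events and n the number at risk. Moving a censoring date later leaves every d unchanged and can only increase n at later events. Each factor stays equal or rises, so the curve and its median cannot fall.

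**Step 2: where the threshold falls.** Twelve weeks is 2.76 months, so scans fall at about 2.76, 5.52 and 8.28 months. Six months lies between the second and third. For progression found at scheduled scans, the criterion therefore turns on whether S(week 24) is above 0.50.

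**Step 3: worked example.** Of 20 patients, 5 progress at week 12, 4 leave after a clean week-12 scan and are known alive beyond week 24, 4 progress at week 24, and 7 are progression-free past 6 months.

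- S(week 12) = 15/20 = 0.75 under both rules.
- Last assessment: 15 − 4 = 11 at risk at week 24. S = 0.75 × 7/11 = 0.48, median 5.5 months, criterion missed.
- Last known alive: 15 at risk. S = 0.75 × 11/15 = 0.55, median beyond 6 months, criterion met.

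Counting the 30-day visit as the last assessment changes nothing here. With the last dose near day 84, that visit falls by day 84 + 37 = 121, before week 24 (day 168).

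A second data set also flips: 4 progress at week 12, 5 leave after that scan and are known alive at 8 months, 5 progress at week 24, and 6 at week 36. S(week 24) is 16/20 × 6/11 = 0.436 against 16/20 × 11/16 = 0.55; the median is 5.52 against 8.28 months.

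**Step 4: expected size.** The documents give neither the rate of leaving without progression nor how much later progression will be captured, so this is a range under assumptions. Each cell is P(median ≥ 6 months), last assessment → last known alive, from 6,000 simulated trials of 20.

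*Model A.* Exponential progression times detected at the next 12-week scan; each patient assigned to leave with the stated probability at Uniform(0, 6) months; vital status known to 24 months. In the no-capture rows, off-treatment deaths are not counted either. In the other rows deaths count, with a 24-month median from progression to death.

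| Leaving | Later progression captured | True median 4 | True median 5 |
|---|---|---|---|
| 0% | any | no difference | no difference |
| 10% | half | 0.120 → 0.124 | 0.330 → 0.335 |
| 10% | none | 0.133 → 0.171 | 0.347 → 0.403 |
| 20% | all | 0.095 → 0.095 | 0.286 → 0.286 |
| 20% | half | 0.149 → 0.166 | 0.368 → 0.392 |
| 20% | none | 0.153 → 0.278 | 0.368 → 0.532 |
| 30% | half | 0.171 → 0.208 | 0.402 → 0.452 |

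If the 30-day visit counts as the last assessment, the 20%/none row starts from 0.187 and 0.423, so its gaps shrink to 0.278 − 0.187 = 0.091 and 0.532 − 0.423 = 0.109. With half captured and that visit counted, the gap at 20% leaving is about 1 to 1.5 points.

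*Model B.* Leaving is a competing exponential; there are no scans after leaving; all deaths count; vital status is known to 12 months after the last entry; median survival after progression is 18 months unless stated.

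| True median | 10% leave | 20% leave | 30% leave |
|---|---|---|---|
| 3 | 0.030 → 0.040 | 0.069 → 0.131 | 0.127 → 0.304 |
| 4 | 0.153 → 0.172 | 0.213 → 0.290 | 0.301 → 0.471 |
| 5 | 0.363 → 0.380 | 0.431 → 0.500 | 0.497 → 0.637 |
| 4 (6-month survival after progression) | 0.152 → 0.156 | 0.236 → 0.254 | 0.324 → 0.364 |

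Only the difference within a cell bears on this point. With nobody leaving, the two rules agree in Model B as well.

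**The case against.** The strongest reply is that the sentence merges a PFS rule and an OS rule: last assessment for progression, last known alive for death. That is plausible, since OS is a listed endpoint without a rule of its own, and nothing says PFS will in fact be censored at the date last known alive. But the sentence sits under the PFS heading, speaks of PFS subjects and never mentions OS, so the reading has to be supplied by the reader.

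The second reply concerns size, and much of it stands. The largest Model A figures need 20% leaving, none of their later progressions or deaths captured, and all known alive at 24 months. Note 10 says follow-up will assess progression, and deaths are PFS events, so this is a worst case. The calendar also has clinical disease assessments between scans and at the 30-day visit, which bring the two dates closer. Contact ends if consent is withdrawn, so for those patients the dates are close; wide gaps arise only in patients who stop treatment but remain in follow-up. The worked examples show that a flip is possible, not that it is likely.

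Third, the stakes are limited. The criterion is exploratory, in a pilot not powered for hypothesis testing. The ORR benchmark, the sample size and the futility rule in section 11.1 do not use PFS censoring. That is correct and limits the weight of the point, but does not supply the missing choice of date.

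**Conclusion.** The concern holds. The stated rule gives two dates for every censored patient, no other section resolves it, and one of the two can bias the curve upward where scheduled scans stop with therapy. The wording defect and the direction of the bias are certain.

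The size is not known. It is zero if nobody leaves without progression or if all later progression is captured. In Model A with half captured, it is under 1 point of success probability at 10% leaving and about 2 points at 20%. It reaches 12 to 16 points at 20% leaving with no capture, and 14 to 18 points in Model B at 30% leaving with long survival after progression. In any single trial of 20, the date alone can decide whether the 6-month criterion is met. The effect is confined to PFS and its exploratory success criterion. This should be corrected, but it does not threaten the primary endpoint.

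**What to change.** Replace the censoring sentence in section 10.5 with:

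> Subjects alive without documented progression are censored at the date of the last disease assessment showing no progression (day 1 if there is no post-baseline assessment); the date last known alive is used only for overall survival.

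The day-1 clause is an added convention for a case section 10.5 does not cover. It would also help to say whether the clinical disease assessments in the calendar, including the 30-day visit, count as disease assessments for this purpose.

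The cost is one sentence. No new data are needed, the date is already named in the plan, and reported PFS follow-up becomes slightly shorter.

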10.6 Assessment Inadequate, Objective Status Unknown

Progression has not been documented and one or more target lesions or other sites of disease have not been assessed or inconsistent methods of assessment were used.

10.7 Bone Marrow Status

Bone marrow status is evaluated as follows:

Positive: Unequivocal morphological, immunohistochemical, or

immunophenotypic evidence of malignancy.

Negative: No aggregates or only a few well-circumscribed lymphoid

aggregates without morphological, immunohistochemical, or

immunophenotypic evidence of malignancy

Indeterminate: Does not qualify for either positive or negative status. *Note this

typically consists of increased number or size of aggregates without morphological, immunohistochemical, or

immunophenotypic atypia.

11.0 STATISTICAL CONSIDERATIONS

The primary objective of this pilot trial is to derive an estimate of the overall response rate (ORR, see section 10.4) in this population. Secondary clinical endpoints will include time to progression, progression-free survival, and safety. The study is not formally powered to reject a specified null hypothesis and as such the sample size is not based on the number of patients needed to reject the null hypothesis under a specified alternative. That said, with 20 patients the estimated ORR will be within 0.11 of the true ORR if the hypothesized ORR is 20%. An ORR of 20% will be taken as a benchmark for success for the primary endpoint of this pilot study. If the observed ORR is at least 20% (4 or more responses among the 20 patients), we would consider this treatment sufficiently meritorious to warrant further study in a future Phase II trial that will formally evaluate potential efficacy. If the true ORR is 10%, then the probability of 4 or more responses among 20 patients is only 0.13; if the true ORR is 30%, then the probability of 4 or more responses among 20 patients is 0.89. As stated above, the sample size for this trial is not based on specific null and alternative hypotheses. That said, if the assumed-true ORR with this regimen is 35%, then 20 patients will provide 86% power to observe a statistically significant (at the one-sided significance level of .15) improvement in ORR compared to the fixed ORR of 15%.

We will also be encouraged if patients have prolonged disease stability/lack of progression that may be observed with a cytostatic biological agent, though this secondary endpoint will deemed exploratory. For this secondary endpoint, a median PFS of ≥ 6 months would also be scored as a pilot success.

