11.1 Stopping Rules

If we see no responses nor any evidence of disease stabilization (as defined above as stable disease ≥6mo) after the first 10 patients, then the trial will be halted for futility. If we see at least one response or capture at least one instance of disease

stabilization ≥6mo among the first 10 patients, then enrollment will continue to goal enrollment of 20 patients.

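### Does the statement that the estimated ORR will be within 0.11 of the truth, given without a confidence level, need correcting?

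*Combined protocol and SAP*

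**What the plan says.** Section 11.0 presents the trial as an estimation exercise: "The primary objective of this pilot trial is to derive an estimate of the overall response rate". It adds that "The study is not formally powered to reject a specified null hypothesis". The statement on precision comes next: "with 20 patients the estimated ORR will be within 0.11 of the true ORR if the hypothesized ORR is 20" percent. No level, probability or method goes with it, and none is given elsewhere in the protocol.

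The same paragraph then sets a decision rule, which begins "If the observed ORR is at least 20% (4 or more responses among the 20 patients". It gives the probability of meeting that rule as 0.13 at a true ORR of 10% and 0.89 at 30%. It also quotes 86% power for 35% against a fixed 15% at a one-sided level of .15.

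The endpoint is defined in section 10.1.1: "Best overall response rate (ORR) which will include complete responses (CR) and partial responses (PR) as measured by standard criteria". Section 11.1 stops the trial if the first 10 patients show neither a response nor stable disease of at least 6 months; otherwise "enrollment will continue to goal enrollment of 20 patients".

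**The concern.** When the aim is to estimate a rate and the sample size does not come from a test, precision is the property that matters most, and this is the only sentence in the plan that describes it. It is phrased as something that will happen, yet a proportion from 20 patients has a standard error of about 0.09 at a true rate of 20%, so no fixed margin as narrow as 0.11 can be assured. A reader who supplies the customary 95% would think the estimate tighter than it is. No confidence interval for the ORR is named either, so nothing in the text corrects that impression. At stake would be an overconfident reading of the pilot result when a later Phase II trial is considered.

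**Working it through.** **Inputs.** n = 20 and hypothesized ORR p = 0.20, with stated margin 0.11 (section 11.0); binary endpoint, CR or PR (section 10.1.1). All 20 patients are taken as evaluable.

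**1. Reproducing 0.11.** SE = √(p(1 − p)/n) = √(0.20 × 0.80/20) = 0.0894. The normal-approximation half-width is z × SE:

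- 70% two-sided (the same z as one-sided .15): 0.093
- 75%: 0.103
- 80%: 1.2816 × 0.0894 = 0.1146, which rounds to 0.11
- 90%: 0.147
- 95%: 1.96 × 0.0894 = 0.175

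Of these levels only 80% gives 0.11. The one-sided .15 quoted later in the section belongs to the power illustration and is not the source. The 86% power figure also reproduces by normal approximation (0.864), so that method is a plausible origin for 0.11. The 80% level remains an inference.

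**2. What the sentence is worth as a probability.** An estimate within 0.11 of 0.20 lies between 0.09 and 0.31, which with 20 patients means 2 to 6 responders. For X ~ Binomial(20, 0.20):

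P(2 ≤ X ≤ 6) = 0.1369 + 0.2054 + 0.2182 + 0.1746 + 0.1091 = 0.844.

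The remainder is P(X ≤ 1) = 0.069 plus P(X ≥ 7) = 0.087, together 0.156, or about 1 in 6.

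**3. Effect of the look after 10 patients.** Take the extreme case in which every trial with 0 responses in 10 stops. It is extreme because lasting stable disease also allows continuation. P(0 of 10) = 0.8^10 = 0.107, and P(2 to 6 responders in the second 10) = 0.623. The probability of reaching 20 patients with an estimate within 0.11 is 0.844 − 0.107 × 0.623 = 0.777. Given that 20 patients are reached, it is 0.777/0.893 = 0.871. So 0.844 is the value for a fixed 20 patients, with 0.777 and 0.871 on either side of it.

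**4. Does anything use 0.11?**

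- Go rule: P(X ≥ 4) = 0.133 at 10% and 0.893 at 30%. Both match the plan, and neither involves 0.11.
- Futility rule: this depends on a count of responses and stable disease, not on 0.11.
- Sample size: section 11.0 says it does not rest on a hypothesis test, and does not say that 0.11 determined it.
- ORR estimate: responders divided by patients, whatever margin was quoted beforehand.

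**5. What the reader of the results would see.** At the go threshold of 4 of 20, the exact 95% interval is 5.7% to 43.7% and the Wilson interval is 8.1% to 41.6%. Either shows the true uncertainty, regardless of the planning sentence.

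**The case for a change.** The best argument for a change is that a trial whose declared purpose is estimation ought to state its precision correctly, and that the repair costs only a sentence. A reader has to guess the level: 80%, 90% and 95% give 0.115, 0.147 and 0.175, and the 95% margin is 53% larger than the 80% one (0.1753/0.1146 = 1.53). The other binomial statements in the paragraph carry probabilities; this one does not. It might be added that the plan names a method for a secondary endpoint in section 10.5, "Kaplan-Meier methodology will be used to estimate event-free curves and corresponding quartiles", but none for the primary.

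Part of this stands. The level is missing, and anyone who assumes 95% would understate the margin.

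The rest is weaker. The neighbouring figures of 0.13, 0.89 and 86% treat results from 20 patients as subject to chance, so few readers would take 0.11 for a guaranteed bound. The comparison with section 10.5 fails, because that section names an estimator for PFS and no confidence interval; the ORR has its estimator too, the proportion with CR or PR. The Phase II decision is tied to the number of responders, not to the quoted margin. Naming an exact 95% interval for the ORR would only write down what an analyst would ordinarily report.

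**Conclusion.** The observation is accurate, but it does not call for a change. The sentence omits its confidence level; the number itself is sound as an 80% half-width (0.1146), and the exact probability behind it is 0.844 for a fixed 20 evaluable patients at a true ORR of 20%. The literal reading fails in 0.156 of such trials, and the 95% margin is 0.175. None of this alters the go rule, its stated probabilities, the futility rule, the sample size or the estimate.

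The conclusion rests on two assumptions: that the 80% level, which the documents do not state, is where 0.11 came from; and that the ORR will be reported with a standard binomial interval, as is usual. If the first is wrong, the exact probability of 0.844 is unchanged. If the second is wrong, the interval can still be computed from the number of responders and the number of patients.

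### The stated 86% power at one-sided 0.15 (ORR 35% against 15%, n = 20) is a large-sample figure that no whole-number response cut-off delivers

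*Combined protocol and SAP*

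**What the plan says.** Section 11.0 describes a single-arm pilot of 20 patients whose primary aim is to estimate ORR. It makes four quantitative statements about that estimate:

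- Precision: "with 20 patients the estimated ORR will be within 0.11 of the true ORR if the hypothesized ORR is 20"%. No confidence level is attached.
- Benchmark: 4 or more responses among 20 would justify a further trial.
- Behaviour of the benchmark: the probability of meeting it is 0.13 at a true ORR of 10%, and "if the true ORR is 30%, then the probability of 4 or more responses among 20 patients is 0.89".
- Power: for a true ORR of 35% against a fixed 15%, "20 patients will provide 86% power to observe a statistically significant (at the one-sided significance level of .15) improvement in ORR". No test and no number of responses is given for this comparison.

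Just before the power statement, the plan says that "the sample size for this trial is not based on specific null and alternative hypotheses". Section 11.1 adds an interim look: with no response and no disease stabilisation of at least 6 months "after the first 10 patients, then the trial will be halted for futility".

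**The concern.** With 20 patients and about 3 responses expected at 15%, the test statistic is coarse. Moving the cut-off by one responder changes both the error rate and the power a good deal, so a level and a power quoted together have to belong to an actual cut-off. The 0.13 and 0.89 in the same paragraph are exact binomial values tied to 4 of 20. The 86% is tied to no count.

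If the pair cannot be attained, the plan publishes a property of its primary endpoint that the trial does not have. A reader also cannot tell whether 5 of 20 would be reported as statistically significant. The only cut-off in the paragraph is 4 of 20, so a reader may attach the 0.15 level to that rule, where it does not belong.

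**Working it through.** **Inputs (Section 11.0).** n = 20; fixed ORR p0 = 0.15; assumed true ORR p1 = 0.35; one-sided level 0.15, so z = 1.036; stated power 0.86.

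**1. Reproducing the stated 86%.**

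Normal approximation without continuity correction:

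- SE under 15%: √(0.15 × 0.85 / 20) = 0.0798
- SE under 35%: √(0.35 × 0.65 / 20) = 0.1067
- Power = Φ[(0.35 − 0.15 − 1.036 × 0.0798) / 0.1067] = Φ(1.099) = 0.864

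Arcsine approximation:

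- Power = Φ[2(arcsin√0.35 − arcsin√0.15)√20 − 1.036] = Φ(2.105 − 1.036) = 0.857

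Both round to 86%. The normal approximation rejects above 20 × (0.15 + 1.036 × 0.0798) = 4.66 responses, which is not an observable count.

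**2. Exact binomial figures at each whole-number cut-off, n = 20.**

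| Reject at | True one-sided error (ORR 15%) | Power (ORR 35%) |
|---|---|---|
| ≥4 | 0.352 | 0.956 |
| ≥5 | 0.170 | 0.882 |
| ≥6 | 0.067 | 0.755 |
| ≥7 | 0.022 | 0.583 |

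The most powerful cut-off with error at or below 0.15 is ≥6, and its power is 75.5%. A randomised exact test also reaches 86%: rejecting 5 of 20 with probability (0.15 − 0.0673) / (0.1702 − 0.0673) = 0.804 gives 0.7546 + 0.804 × (0.8818 − 0.7546) = 0.857. Nothing in the plan suggests a randomised decision.

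**3. The unnamed test decides the result at 5 of 20.**

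- Score test: z = (0.25 − 0.15) / 0.0798 = 1.252, p = 0.105, significant at 0.15.
- Mid-p: p = 0.119, significant.
- Exact binomial: p = 0.170, not significant.

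**4. The 4-of-20 benchmark at the rates in the power sentence.** The exact probabilities at 10% and 30% are 0.133 and 0.893, so the plan's 0.13 and 0.89 are correct. At 15% and 35% they are 0.352 and 0.956, and the plan gives neither.

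The interim look lowers these slightly. On the strictest reading, the trial stops at 0 responses in the first 10 and ignores stable disease, with those patients' response status taken as final. Then P(go) = P(≥4 of 20) − P(0 of 10) × P(≥4 of the next 10):

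- At 15%: 0.3523 − 0.1969 × 0.0500 = 0.342
- At 35%: 0.9556 − 0.0135 × 0.4862 = 0.949

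Stable disease of at least 6 months also keeps the trial open, so the true values lie between the two sets.

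**5. The precision figure.** SE at ORR 20% = √(0.2 × 0.8 / 20) = 0.0894.

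- 80% half-width: 1.282 × 0.0894 = 0.115
- 95% half-width: 1.960 × 0.0894 = 0.175
- Confidence matching 0.11: 0.11 / 0.0894 = 1.230, or 78.1%
- Exact probability that the estimate falls within 0.11 of 0.20 (2 to 6 responses): 0.844

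**The case against.** The 86% is not a slip of calculation. A standard one-sample formula with the plan's own inputs returns it. If the test meant is the uncorrected score test, which fits 86% well, then 5 of 20 is significant, the true power is 88%, and the plan slightly understates power. What is left is a true error of 0.170 against a nominal 0.15. The 75% figure applies only if an exact test was meant. Nothing depends on the sentence in any case: the plan twice disclaims formal powering, and 5 of 20 already passes the 4-of-20 benchmark. For an estimation pilot, the unlabelled 0.11 arguably matters more.

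Much of this stands. The formula does return 86%, power is not overstated under a score test, and the sentence drives no decision. But the disclaimer concerns how the sample size was chosen. It does not make the published pair of level and power attainable, and the plan does not say that the figure is approximate. Under either test one of the two figures is wrong for the trial as run: the level under a score test, the power under an exact test. The point about priority is fair, and the precision label belongs in the same correction. The extra benchmark probabilities are useful but optional.

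**Conclusion.** The concern holds. With 20 patients, no fixed response cut-off gives 86% power at 35% with a true one-sided error of at most 0.15 at 15%. The attainable pairs either side are 0.067 with 75.5% (≥6 of 20) and 0.170 with 88.2% (≥5 of 20). Against the stated figures, that is a shortfall of about 10.5 points in power or an excess of 0.02 in the error rate, depending on the test.

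The exact figures assume 20 evaluable patients with independent responses and no interim stop. Stopping at 0 of 10 responses hardly changes them: 0.168 and 0.878 at ≥5, 0.067 and 0.753 at ≥6. That the 86% came from a large-sample formula is an inference, since the plan names no method.

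The point should be fixed, but its reach is limited to the description of the design. The sample size, the benchmark and the futility rule are unaffected.

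**What to change.** In Section 11.0, either delete the power sentence, which fits the plan's statement that the sample size does not rest on hypotheses, or replace it with one of the following. The sponsor chooses the test.

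- **Option A:** By an exact one-sided binomial test against a fixed ORR of 15%, 6 or more responses among 20 is significant at 0.15 (true error 0.067), with 75% power at a true ORR of 35%.
- **Option B:** Rejecting at 5 or more responses among 20, for example by a score test, has a true error of 0.17 and 88% power at a true ORR of 35%.

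If the sentence stays, say that the calculation is illustrative and separate from the 4-of-20 benchmark. Label the 0.11 as about 80% confidence, or give ±0.18 at 95%.

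Optionally, add the benchmark's probabilities at 15% and 35% beside the 0.13 and 0.89: 0.35 and 0.96, or 0.34 and 0.95 if the futility stop acts on responses alone.

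The cost is wording only. The stated figures become less favourable: lower power under A, a true error above 0.15 under B, and a wider precision figure if 95% is used. For scale, an exact test first reaches 86% power within 0.15 at 23 patients (≥6 of 23: error 0.119, power 0.869). No change to the sample size is proposed.
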